9 SAFETY MANAGEMENT

This project is associated with minimal risk. Therefore, the investigators have not incorporated a formal Data and Safety Monitoring Board. The project will be monitored by Drs. [name], [name], [name], and [name]. [name] will meet with the Project Director on a weekly basis to monitor any adverse effects reported by study participants. Drs. [name], [name], [name], and [name] will meet quarterly to monitor safety concerns. Study participants will be instructed to call the Project Director if they experience any problems that they attribute to study participation. To make it easy for participants to contact the Project Director if needed, the investigators will give all participants a magnetized card with the Project Director's name and telephone number to place on their refrigerator. The Project Director will record each problem reported in a database created for that purpose. [name] and the Project Director will discuss all problems reported on a weekly basis. Each event reported will be classified into one of the following categories:

1. Mild Adverse Event – Event results in mild or transient discomfort, not requiring intervention or treatment; does not limit or interfere with daily activities.
2. Moderate Adverse Event – Event is sufficiently discomforting so as to limit or interfere with daily activities; may require interventional treatment.
3. Severe and Undesirable Adverse Event – Event results in significant symptoms that prevents normal daily

The interventions the investigators will test involve minimal risk. Therefore, the investigators have no plans to withdraw individual participants for any reason. However, if a participant becomes upset concerning any study procedures, the investigators will ensure that they understand that they have the right to withdraw from the study at any time, without penalty.

10 DATA COLLECTION AND MANAGMENT

Data will be collected primarily via telephone interviews, and self-administered, Internet-based surveys using REDCap and Qualtrics. All individuals involved in the study will be trained as to the confidential nature of all data collected. In addition, all personnel will complete ethics training in accordance with IRB policy before they are

allowed to have any contact with study participants or data obtained from study participants. All participants will be assigned a unique identifying number that will allow the investigators to track them over the course of the study. A key linking participants' names and contact information to this unique identifier will be stored in an encrypted file stored on a password protected computer housed behind a firewall on the UNC-CH computer system. Only the principal investigator and project director will have access to this encrypted file. Participants will not be identified in any report or publication about this study. All sharing of research documents between research team members will occur via a secure online drive. All information stored in computer files will be password-protected and passwords will be changed on a regular basis. Information sent by clinical coordinators to the central project office as part of the recruitment process will be sent to a fax machine located in a private office, dedicated to this research project. The office will be locked when study personnel are not present. All information collected that contains the names of study participants will be kept in locked filing cabinets when not in use..

The names of patients identified at participating clinics and the date of their next visit will be entered into an on-line database using the UNC REDCap Software. Data entered using the REDCap system are maintained on secure, HIPAA-compliant servers. Each clinic site will have access only to information entered at their site. If a hard copy of information in this database is needed to facilitate recruitment, staff working on the project will be instructed to shred the hard copy at the end of each clinic day.

11 RECRUITMENT STRATEGY

Please see Section 3.3 "Study Duration, Enrollment and Number of Subjects"

12 CONSENT PROCESS

We will obtain written informed consent from participants. We will go over the consent form with potential participants, solicit questions they may have about the study, obtain the participant's signature on the consent form, and provide the participant with a copy of the consent form. Consent will be obtained by clinical coordinators working at clinic sites and research assistants and the project director working in the central project office at the University of North Carolina at Chapel Hill. We will emphasize to all potential participants that they are not obligated to take part in the study and that they may decline study participation for any reason, and without providing a reason, without any negative consequences. The investigators do not plan to enroll individuals who are decisionally-impaired or lack sufficient English-language proficiency to understand study procedures and the potential risks and benefits associated with participation.

13 PLANS FOR PUBLICATION

The investigators plan to publish up to three papers reporting study findings in the peer-reviewed literature.

15 APPENDIX

Figure 1. Conceptual Framework

[figure not shown]

Table 1. Summary of study measures

Variable	Time Assessed	Data Collection Instrument	Range	Baseline Alpha
Knowledge	B, 6W, 3M, 6M	Telephone Interview	0 to 100	0.84
Values	B, 6W, 3M, 6M	Self-Administered Questionnaire	-15 to +15	0.67
DMARD Usage	B, 6W, 3M, 6M	Self-Administered Questionnaire	0=Not using any DMARDS 1=Using 1+ DMARDS	NA
Informed Decision-Making	B, 6W, 3M, 6M	Composite measure based on Knowledge, Values and DMARD Usage	0=Did not meet criteria 1=Met criteria	NA
Gist Reasoning Ability:				
Complex Abstraction	B, 6W, 3M, 6M	Self-Administered Questionnaire†	0 to 8	NA
Lesson Quality	B, 6W, 3M, 6M	Self-Administered Questionnaire†	0 to 5	NA
Selective Learning	B, 6W, 3M, 6M	Telephone Interview	0 to 264	0.67
Verbatim Recall	6W	Telephone Interview	0 to 2	0.14††
Medication Self-Management Knowledge	6M	Telephone Interview	0 to 100	0.36

Variable	Time Assessed	Data Collection Instrument	Range	Baseline Alpha
Information Seeking:				
Use of RA Self-Management Website	6M	NA	0=Never accessed website 1=Accessed website 1+ times	NA
Participation in BetterChoices, Better Health	6M	NA	0=Did not participate in all 6 sessions 1=Participated in all 6 sessions	NA
Treatment Satisfaction:				
Global	B, 6W, 6M	Self-Administered Questionnaire	0 to 100	0.83
Effectiveness	B, 6W, 6M	Self-Administered Questionnaire	0 to 100	0.90
Side-Effects	B, 6W, 6M	Self-Administered Questionnaire	0 to 100	0.82
Convenience	B, 6W, 6M	Self-Administered Questionnaire	0 to 100	0.86

Variable	Time Assessed	Data Collection Instrument	Range	Baseline Alpha	
Satisfaction with Medication Information: Overall					
	B, 6W, 6M	Self-Administered Questionnaire	0 to 17	0.88	
	Actions	B, 6W, 6M	Self-Administered Questionnaire	0 to 9	0.78
Problems	B, 6W, 6M	Self-Administered Questionnaire	0 to 8	0.85	
Arthritis Self-Efficacy	B, 6W, 6M	Self-Administered Questionnaire	0 to 100	0.87	
Illness Intrusiveness: Overall					
	B, 6M	Self-Administered Questionnaire	0 to 100	0.90	
	Relationships	B, 6M	Self-Administered Questionnaire	0 to 100	0.85
	Instrumental	B, 6M	Self-Administered Questionnaire	0 to 100	0.71
Intimacy	B, 6M	Self-Administered Questionnaire	0 to 100	0.82	
Health Distress	B, 6M	Self-Administered Questionnaire	0 to 5	0.91	

Variable	Time Assessed	Data Collection Instrument	Range	Baseline Alpha
Depression	B, 6M	Self-Administered Questionnaire	T-Score: Mean =50, SD=10 in reference population	NA
Fatigue	B, 6M	Self-Administered Questionnaire	T-Score: Mean =50, SD=10 in reference population	NA
Disease Activity	B, 6W, 3M, 6M	Self-Administered Questionnaire	0 to 10	0.81
Global Health Status	B, 6M	Self-Administered Questionnaire	1 to 4	NA
Subjective Health Literacy	B, 6M	Self-Administered Questionnaire	0 to 4	0.80
Objective Health Literacy	B, 6M	Telephone Interview	0 to 100	Version A: 0.60 Version B: 0.49
Medication Adherence	B, 6M	Self-Administered Questionnaire	0 to 100	NA

†A separate online, self-administered questionnaire was used to assess Gist Reasoning Ability. It was completed before participants did the questionnaire assessing other study measures.

††This variable was only assessed at the 6-week follow-up. Therefore, the alpha reported is for that time point.

NOTE: For all variables except Global Health Status, higher values reflect higher levels of the attribute measured. For Global Health Status, higher values reflect poorer health status.

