In the main analysis, the investigators will use an *intention-to-treat* strategy, with individuals included in the analysis based on random group assignment, without regard to whether they were actually exposed to the intervention. However, the investigators will only include participants with nonmissing data at the 6-month follow-up. In addition to the main analyses, the investigators will perform three sets of sensitivity analyses to

assess the robustness of the findings. The first set of sensitivity analyses will use an *as-treated* approach and include only people with nonmissing data at the 6-month follow-up. Individuals will be included in this analysis only if they actively participated in the interventions. For the DrugFactsBox[®]/Other CMI groups, the investigators defined active participation as viewing at least one page on the DrugFactsBox[®]/Other CMI website. For the SMART group, the investigators will define active participation as attending at least 3 of the 4 training sessions. Note that all individuals in the No SMART group will be included in the *as-treated* analyses because they will not have an opportunity to participate in any training. In the second set of sensitivity analyses, the investigators will use an *intention-to-treat* approach and impute missing data using the last-observation-carried forward method for individuals who do not complete the 6-month follow-up. In the final set of sensitivity analyses, the investigators will use as *as-treated* approach and impute missing data using the last-observation-carried forward method.

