Secondary Analyses: The investigators will use the same analytic strategy to examine the effect of the intervention on 18 secondary outcomes assessed at the 6-month follow-up: Medication Self-Management Knowledge, Selective Learning, Complex Abstraction, Lesson Quality, Use of the RA Self-Management Website, Participation in the BetterChoices,BetterHealth program, Self-Efficacy, Overall Medication Satisfaction, Global Treatment Satisfaction, Medication Adherence, Objective Health Literacy, Subjective Health Literacy, Disease Activity, Illness Intrusion, Illness Distress, Global Health, Depression, and Fatigue. In these analyses, the investigators will use either logistic or linear regression, depending on the measurement properties of the outcome variable. Due to the number of endpoints examined in these secondary analyses, the investigators will use the Hochberg method to adjust for the potential inflation of Type I error.⁸⁵

Exploratory Analyses: The investigators will use the same analytic strategy to evaluate intervention effects at the 6-week and 3-month follow-ups. However, these analyses will be considered exploratory and are designed to capture any transient intervention effects that may occur.

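### Carrying the last observation forward means carrying baseline forward for eight secondary outcomes, and cannot be done for Medication Self-Management Knowledge, because of when Table 1 schedules them

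*Combined protocol and SAP*

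**What the plan says.** Section 6.3 (Statistical Methods) sets the main analysis by randomised group, but "the investigators will only include participants with nonmissing data at the 6-month follow-up". Missing data are then handled only in the sensitivity sets. The second set keeps intention-to-treat and will "impute missing data using the last-observation-carried forward method for individuals who do not complete the 6-month follow-up". The last does the same on an as-treated basis: "In the final set of sensitivity analyses, the investigators will use as *as-treated* approach".

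Under Secondary Analyses, the same section says it will use "the same analytic strategy to examine the effect of the intervention on 18 secondary outcomes assessed at the 6-month follow-up". It makes no exception for any outcome.

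Table 1 (section 15, Appendix) gives the schedules. A typical row among the eight is "Medication Adherence B, 6M Self-Administered Questionnaire". The ninth outcome reads "Medication Self-Management Knowledge 6M Telephone Interview".

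**The concern.** LOCF needs a value taken between baseline and the missing visit if it is to say anything about the participant after randomisation. Where there is none, the method imputes the baseline score. A participant who answered at 6 weeks and 3 months but missed 6 months is then treated, on these outcomes, as if nothing had happened since randomisation. Where there is no baseline either, the rule cannot be executed and the analyst must improvise.

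These sets are meant to show whether the completers' result is robust. For the eight outcomes they pull a real effect toward zero by construction. If dropout differs between groups while scores change in all groups, they can also produce a difference where none exists. The SMART groups are asked to attend four live sessions and the others are not, so unequal dropout is possible.

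**Working it through.** **The plan's own figure.** Section 6.4 gives 300 participants (75 per arm), 80% power, 60% v 35%, two-sided 0.05 and 15% attrition. With pooled variance under the null:

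- n = (1.96 × √(2 × 0.475 × 0.525) + 0.842 × √(0.6 × 0.4 + 0.35 × 0.65))² / 0.25² ≈ 61.4, so 62 per arm.
- 62 / 0.85 = 72.9, so 73 per arm and 292 in total.

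This reproduces as a comparison of one arm with another and is not in dispute. Only the 15% attrition is used below.

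**Schedules.** The 18 outcomes listed in section 6.3, matched to Table 1:

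- Baseline, 6 weeks, 3 months, 6 months (4): Selective Learning, Complex Abstraction, Lesson Quality, Disease Activity.
- Baseline, 6 weeks, 6 months (3): Self-Efficacy and the two satisfaction outcomes.
- Baseline and 6 months only (8): Medication Adherence, Objective and Subjective Health Literacy, Illness Intrusiveness, Health Distress (called Illness Distress in section 6.3), Global Health, Depression, Fatigue.
- 6 months only (3): Medication Self-Management Knowledge, use of the self-management website, participation in the self-management class.

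4 + 3 + 8 + 3 = 18. Of the last three, section 5.1 has the website and class outcomes tracked by web analytics and class records, so loss to follow-up need not make them missing. Medication Self-Management Knowledge is collected by telephone interview and can be missing. The affected outcomes are therefore 8 + 1 = 9.

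**Participants affected.** 0.15 × 300 = 45 in total, or 0.15 × 75 ≈ 11 per arm, on each of the eight.

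**Dilution.** Compare the two levels of one intervention, 150 v 150, adjusting for baseline. Assume a baseline-to-6-month correlation of 0.6, scores in SD units, and dropouts who would have responded like completers. With dropout p, the expected LOCF effect is (1 − p) × the true effect:

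- p = 0.15: 0.85 × 0.30 = 0.255
- p = 0.05: 0.95 × 0.30 = 0.285
- p = 0.25: 0.75 × 0.30 = 0.225

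Standard error at p = 0.15:

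- Fitted baseline slope: 0.6 + 0.15 × 0.4 = 0.66.
- Residual variance: 0.85 × (0.64 + 0.06²) + 0.15 × 0.34² = 0.564.
- SE: √(0.564 × 2/150) = 0.087. Completers alone give 0.8 × √(2/127.5) = 0.100.

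The bias is 0.045 / 0.087 ≈ 0.52 SE, which implies about 92% coverage. Simulated trials of 300 gave an estimate of about 0.25 and about 91% coverage under LOCF, and 0.29 to 0.30 and 95% in completers.

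**False positives with no true effect.** Bias = −(difference in dropout) × (drift common to both groups). Drift adds drift² × 0.15 × 0.85 to the residual variance, giving SE 0.089 at 0.5 SD and 0.087 at 0.2 SD.

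| Assumed drift | Dropout | Bias | Bias / SE | Rejection rate |
|---|---|---|---|---|
| 0.5 SD | 10% v 20% | −0.05 | 0.56 | about 9% |
| 0.5 SD | 5% v 25% | −0.10 | 1.12 | about 20% |
| 0.2 SD | 10% v 20% | −0.02 | 0.23 | about 6% |
| 0.2 SD | 5% v 25% | −0.04 | 0.46 | about 7% |

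Simulation agrees within a point: about 9%, 19–20%, 5–6% and 7–8%. With equal 15% dropout, or with zero drift, the rate stays near 5%. The completers' analysis stays near 5% throughout.

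**The case against.** The strongest case on the other side has five parts.

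1. *Section 6.3 never says outright that the LOCF sets extend to the secondary outcomes.* True; this is an inference. But the sensitivity sets are part of the strategy described, and no exception is stated. If they were not meant to apply, the secondary outcomes have no missing-data sensitivity analysis at all. Either way the section needs a sentence.
2. *The entry for Medication Self-Management Knowledge may be incomplete.* Table 1 prints 0.36 for it in the Baseline Alpha column without a footnote, whereas Verbatim Recall has a footnote saying that its alpha is from 6 weeks. This stands: the sponsor should confirm the schedule. As printed, there is nothing to carry.
3. *The larger false-positive rates depend on chosen inputs.* This also stands. The documents give neither a drift nor any split of attrition by group, and the rates are before the planned Hochberg adjustment. A reader might infer that LOCF inflates error in this trial generally, or that the SMART groups will lose more people. The documents support neither.
4. *A sound result would seldom be reversed.* For a true 0.30 SD effect without drift, power is about 82% under LOCF and 84% in completers. That is fair: the harm is a diluted estimate with too narrow an interval around it. The plan also sets no rule for declaring a result robust or not.
5. *LOCF is a general weakness, so why single these out?* Anyone lost before 6 weeks has baseline carried forward on every outcome measured at baseline. The difference is that for these eight it happens to every dropout, whenever they leave.

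Two other inferences go too far. Three outcomes are listed only at 6 months, but two are tracked passively, so it does not follow that LOCF fails for all three. And although Objective Health Literacy uses a different test version at 6 months, section 5.1 assigns versions at random and balances them, so carrying the other version adds noise rather than an expected difference between groups.

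**Conclusion.** The point holds. On the natural reading of section 6.3, the two LOCF sets become baseline carried forward for eight of the 18 secondary outcomes and cannot be run for a ninth, subject to confirmation of its schedule.

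The dilution needs no unequal dropout. It follows from 15% attrition and the assumption that dropouts respond like completers; the coverage figure also uses the assumed correlation of 0.6. The false-positive risk is conditional on both unequal dropout and common drift, and is small at modest drift.

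A reader might take this as a threat to the main conclusions. It is not. Informed Decision-Making is scheduled at baseline, 6 weeks, 3 months and 6 months, and the main analysis of every outcome uses completers. Only sensitivity analyses of secondary outcomes are affected, so the priority is low to moderate.

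**What to change.** In section 6.3, state whether the sensitivity sets apply to the secondary outcomes. For the nine outcomes named above, replace LOCF in both sets with multiple imputation by arm. Predictors would be the outcome's own baseline value (where one exists) and measures already collected at 6 weeks and 3 months, such as Knowledge and Disease Activity at both visits and Self-Efficacy and Treatment Satisfaction at 6 weeks. With about 64 completers per arm (0.85 × 75), the predictor list should be short and fixed in advance.

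Confirm in Table 1 whether Medication Self-Management Knowledge was given at baseline, and footnote its alpha accordingly. State that the two tracked behaviours are scored from tracking records whether or not the 6-month follow-up is completed.

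The cost is wording and a standard imputation step in SAS, with no new data. Intervals will be slightly wider than under LOCF. Imputation assumes that missingness is explained by the observed data, and the plan should say so.
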